12. DATA AND SAFETY MONITORING

In compliance with the Washington University Institutional Data and Safety Monitoring Plan, the Principal Investigator will provide a Data and Safety Monitoring (DSM) report to the Washington University Quality Assurance and Safety Monitoring Committee (QASMC) semi-annually beginning six months after accrual has opened (if at least five patients have been enrolled) or one year after accrual has opened (if fewer than five patients have been enrolled at the six-month mark).

During the phase I dose de-escalation, the Principal Investigator will review all patient data at least monthly (or before each dose de-escalation if occurring sooner than monthly), and provide a semi-annual report to the Quality Assurance and Safety Monitoring Committee (QASMC). During the phase II, the Principal Investigator will review all patient data at least every six months, and provide a semi-annual report to the QASMC. This report will include:

- HRPO protocol number, protocol title, Principal Investigator name, data coordinator name, regulatory coordinator name, and statistician
- Date of initial HRPO approval, date of most recent consent HRPO approval/revision, date of HRPO expiration, date of most recent QA audit, study status, and phase of study
- History of study including summary of substantive amendments; summary of accrual suspensions including start/stop dates and reason; and summary of protocol exceptions, error, or breach of confidentiality including start/stop dates and reason
- Study-wide target accrual and study-wide actual accrual
- Protocol activation date
- Average rate of accrual observed in year 1, year 2, and subsequent years

- Expected accrual end date and accrual by cohort
- Objectives of protocol with supporting data and list the number of participants who have met each objective
- Measures of efficacy
- Early stopping rules with supporting data and list the number of participants who have met the early stopping rules
- Summary of toxicities separated by cohorts with the number of dose-limiting toxicities indicated
- Abstract submissions/publications
- Summary of any recent literature that may affect the safety or ethics of the study

The study principal investigator and Research Patient Coordinator will monitor for serious toxicities on an ongoing basis. Once the principal investigator or Research Patient Coordinator becomes aware of an adverse event, the AE will be reported to the HRPO and QASMC according to institutional guidelines.

Version 2/12/2021

APPENDIX A: QST protocol

Quantitative sensory testing will be performed on the dorsal mid-foot, bilaterally. The volar side of the dominant arm will serve as control area.

A description of the QST procedures follows:

Thermal detection and thermal pain thresholds

Equipment: The Thermal Sensory Analyzer (TSA-II platform - Medoc, Ramat Yishai, Israel) will be used to determine thermal detection and pain thresholds. This equipment is used globally for functional assessment of pain and temperature-conducting nerve fibers (C and A-delta fibers).

Method and Background: Using the thermal sensory analyzer, cold and warm detection thresholds (CDT and WDT, respectively), as well as cold and heat pain thresholds (CPT and HPT, respectively) will be determined [48, 49]. The thermode with contact area of 9.0 cm² is applied to the tested site, and all thresholds are determined by continuous ramping of temperature from 32°C baseline temperature by 1°C/s until the subject presses the 'stop' button. Cut-off temperatures are 0°C and 50°C, to minimize thermal damage to the skin. The baseline temperature to which the thermode returns before each test is 32°C. The average threshold is calculated from three measurements in each area.

Determination of mechanical detection threshold (MDT)

Equipment: A set of standardised von Frey filaments (0.25, 0.5, 1, 2, 4, 8, 16, 32, 64, 128 and 256mN). The contact area of the hairs with the skin is of uniform size (<1 mm²) and texture.

Methods and Background: Standardised von Frey filaments will be used in a modified "method of limits" manner using 3 series of increasing and decreasing stimulus intensities to determine the geometric average as the tactile detection threshold of the affected and unaffected skin areas [50].

Von Frey filaments of different stimulus intensities are used to determine the tactile detection thresholds. A filament eliciting 16mN force* is applied first, followed by filaments of consecutively lower intensity until the patient cannot detect the stimulus being applied. This respective force represents the first threshold value. The order in which the stimuli are applied is then reversed and stimuli of consecutively greater intensity are applied until sensation is detected (this intensity becomes the second value). Again filaments with decreasing intensity are applied until in total 3 upper and lower values of detection are fulfilled from which the mechanical detection threshold can be determined.

* In case the first von Frey filament with an intensity of 16mN is not detected, the next highest intensity filament which can be detected must be used as a starting intensity. However, the relevant force of this stimulus is not documented. Filaments with consecutively lower intensity are applied until the patient cannot detect the stimulus being applied. The procedure is followed as above; until in total 3 upper and lower values of detection are fulfilled from which the mechanical detection threshold can be determined.

Determination of mechanical pain thresholds (MPT)

Equipment: A set of standardized weighted metal probes (Nervetest, MRC systems) exerting pressure of 8, 16, 32, 64, 128, 256 and 512 mN.

Methods and Background:

The standardized metal probes will be used in a modified method of levels manner, 3 series of increasing stimulus intensities to detect the mechanical pain threshold. Beginning with an applied force of 8mN, stimuli increase in intensity until the sensation induced by increased pressure can be described as 'painful'.

The corresponding force is used to represent the first MPT value. The procedure is then repeated a total of 3 times and until a total of 3 values are obtained, from which the mean MPT is determined.

Determination of vibration detection thresholds (VDT)

Equipment: A standard tuning fork.

Methods and Background:

The tuning fork will be applied at the lateral malleolus, and vibration detection threshold (the moment patient stops feeling the vibration of the tuning fork applied to the skin) will be measured on a scale of 1-8. The test will be repeated a total 3 times. VDT is determined as an average of the three measures.

Determination of wind-up ratio (WUR)

Equipment: A standardized weighted metal probes (Nervetest, MRC systems) exerting pressure of 256mN.

Methods and Background: In this test a pinprick (256mN) is first applied singularly. After that a series of 10 identical pinprick stimuli are applied with a frequency of 1 s^{-1} within an area of 1 cm^2 . Immediately following the single stimulus and series of stimuli, an evaluation of the sensation must be provided according to NRS (0-10, '0': 'no pain', '10': 'worst pain imaginable'). A ratio is calculated using these values. This procedure will be repeated 3 times. A geometric average of the 'wind-up' is calculated from the two ratios (Price, Hu et al. 1977, Magerl, Wilk et al. 1998).

Supplements

Table 1: Lidocaine dosing scheme based on IBW

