9.2. Secondary Outcome Measures

1. Occurrence of Grade 2+ peripheral neuropathy during treatment, measured by NCI-CTC Peripheral Neuropathy Grading;

- 2. Time to event (Grade 2+ peripheral neuropathy)
- 3. Change in CIPN score (on EORTC QLQ-CIPN20 tool) over time until last follow-up;
- 4. Magnitude of sensory disturbances on QST (change from baseline to last follow-up);

5. Changes in NPSI descriptors of neuropathic pain over time from baseline to last follow-up (NPSI will be administered separately for pain in feet and for pain in hands).

7. Change in Mental and Physical summary scores on RAND-12 questionnaire [37] from baseline to last follow-up;

- 8. Pain intensity on 0-10 numerical rating scale at each treatment day, and last follow-up.
- 9. The cumulative dose of oxaliplatin over the course (up to 12 cycles) of mFOLFOX6

10. Two-year progression-free and overall survival determined by medical record review.

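### The wind-up ratio rule in Appendix A gives conflicting counts of ratios and cannot be computed for some ratings of 0; the document states neither the ratio's direction nor a zero rule

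*Combined protocol and SAP*

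**What the plan says.** In Appendix A, the wind-up test applies one 256 mN pinprick and then a train of ten identical ones. The patient rates each for pain on a 0-10 scale on which 0 is a permitted answer. The rule for turning ratings into a result has three parts:

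- "A ratio is calculated using these values", without saying which rating is the numerator.
- "This procedure will be repeated 3 times".
- The summary is a geometric average that "is calculated from the two ratios".

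The same appendix averages three measurements for the thermal thresholds, three values for the mechanical pain threshold (MPT) and three for vibration. The MPT probes are described as "exerting pressure of 8, 16, 32, 64, 128, 256 and 512 mN", so they go above the 256 mN used for wind-up.

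The Synopsis and Section 6.1 list wind-up among the quantitative sensory tests (QST). Section 9.2 makes the change in QST between baseline and the final follow-up secondary outcome 4. Neither Appendix A nor Sections 9 and 10 say what to do when a rating is 0.

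**The concern.** Two adjacent sentences disagree on how many ratios enter the average, so two analysts with the same ratings could report different values.

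Separately, a ratio needs a non-zero denominator, and a geometric average is useful only if every ratio is positive. Zeros are foreseeable from the protocol itself. A patient whose pain threshold lies above 256 mN, which the MPT probes allow for, would rate the single pinprick 0. Section 1.2 also names reduced mechanical sensation among the signs of this neuropathy.

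If uncomputable values were left out, the omission would be tied to low pinprick pain. Lidocaine is meant to prevent the neuropathy that can cause such loss, so the omission could differ by arm and bias the comparison. Settling the rule after the data are seen would be undesirable, more so with only 30 randomized patients.

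**Working it through.** **1. Count of ratios.** Each run gives one single rating and one series rating, hence one ratio.

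| Reading | Ratios |
|---|---|
| Three runs in total | 3 |
| A first run plus three repeats | 4 |
| Two as the two ratings within a run | 1 |
| Two as the two feet | 2, but Appendix A does not say so, and Section 6.1 tests three areas (both feet and a forearm control) |

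The stated two is reached only by the reading that the text does not give.

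**2. Does the count matter?** Take series/single ratings of 3/1, 4/2 and 6/2, so the ratios are 3, 2 and 3.

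- All three: (3 × 2 × 3)^(1/3) = 18^(1/3) = 2.62.
- First two: (3 × 2)^(1/2) = 2.45.
- First and third: (3 × 3)^(1/2) = 3.00.

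With independent repeats, averaging two log ratios instead of three raises the standard error by √(3/2) = 1.22.

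**3. Zeros.** Assume the usual direction, series divided by single.

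- Single = 0: the ratio is x/0 or 0/0, which is undefined.
- Series = 0 with single > 0: the ratio is 0, so the geometric average is 0 and its log is undefined.

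Reversing the direction swaps the two cases and removes neither.

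**4. How often?** The documents give no frequency, so p, the chance that a single pinprick is rated 0, is an assumption. With three independent repeats:

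| p | At least one undefined, 1 − (1 − p)³ | All three undefined, p³ |
|---|---|---|
| 10% | 1 − 0.729 = 27.1% | 0.1% |
| 20% | 1 − 0.512 = 48.8% | 0.8% |
| 30% | 1 − 0.343 = 65.7% | 2.7% |

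If repeats are fully correlated, all three are zero together and both columns equal p: 10%, 20% and 30%. Repeats in one patient at one visit should lie between these extremes.

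**5. In whom?** A simulation used assumed ratings (between-patient SD 1.2, within-patient SD 0.8, rounded to the 0-10 scale). For mean single-pinprick pain of 1, 2, 3 and 4, at least one of three ratios was undefined in 55%, 27%, 9% and 2% of patients. The SDs are illustrative, but the pattern is that the problem sits with patients who feel little pinprick pain.

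**The case against.** **The word two may be a slip for three.** This is plausible, because the other repeated tests averaged in the appendix use all three values. A reader might infer that one repeat is discarded and collected data wasted. The document prescribes no such step. What stands is that the count must be corrected.

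**No exclusion is planned.** A reader might infer that patients with low pain will drop out of this analysis. Nothing says that undefined ratios are excluded, and they could be handled ad hoc, for instance by adding a constant. Section 6.1 also refers to an established QST protocol, and the wind-up text cites further sources, which may hold a zero rule. The supportable claim is that this document states none.

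**The percentages can be pushed too far.** A change score needs two visits, and a reader might infer a loss of 1 − (1 − p)⁶ = 47%, 74% or 88% for p of 10%, 20% or 30%. That requires all six ratios to be independent and one undefined ratio to void the whole score. If the remaining ratios are averaged instead, with the same independence, the loss is 1 − (1 − p³)² = 0.2%, 1.6% or 5.3%. The documents support neither as a forecast.

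**The direction of bias is open.** Section 1.2 describes the neuropathy as typically painful, with allodynia as well as sensory loss, so pinprick ratings may rise or fall. The calculations apply the same p to everyone and so show no difference between arms.

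**The reach is small.** Wind-up is one of eight QST parameters in Section 6.1, and secondary outcome 4 does not name it. This stands.

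**Conclusion.** The point holds as a minor one about a stated rule that conflicts with itself and cannot always be computed. The conflict between three repeats and two ratios is explicit. The failure at zero follows from the scale and the geometric average, whichever way the ratio runs.

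Bias is conditional: it needs undefined values to be excluded and zeros to occur at different rates in the two arms. Its direction and size cannot be derived from the documents. The figures of 27-66% (at least one ratio undefined) and 0.1-2.7% (all three) rest on an assumed p of 10-30%, the series/single direction, three ratios and independent repeats. The consequence is confined to one component of secondary outcome 4. The primary outcome and the sample size are untouched.

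**What to change.** Amend the wind-up text in Appendix A, or the analysis plan, before unblinding:

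1. Use all three repeats.
2. Define the wind-up ratio as the mean of the three series ratings divided by the mean of the three single ratings.
3. Add the same small pre-specified constant to both means for every patient and visit. Adding it only when the single mean is 0 would leave the log undefined when the series mean is 0 and the single mean is positive.
4. Analyse the log ratio.
5. Use series minus single, which is always defined, as a sensitivity analysis.
6. Report the number of zero means by arm and visit.

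This needs no new measurements, provided the individual ratings are recorded. There are two downsides. The value is no longer a geometric mean of separate ratios. The constant also pulls the ratio toward 1, slightly when the means are not small: with a constant of 0.1, means of 4 and 2 give 4.1/2.1 = 1.95 instead of 2. When the single mean is 0 the result depends heavily on the constant. A series mean of 3 gives 3.1/0.1 = 31 with a constant of 0.1, but 3.2/0.2 = 16 with 0.2. That is why items 5 and 6 belong in the plan.

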APPENDIX B: Questionnaires

- Veteran's RAND-12 (VR-12)
- Hospital Anxiety and Depression Scale (HADS)
- Neuropathic Pain Symptom Inventory (NPSI)
- Brief Pain Inventory (BPI)

APPENDIX C: Cognitive tests

- Trail Making Test A (TMT A) and Trail Making Test B (TMT B)
- Color Word Matching Stroop Test (CWMST).

APPENDIX D: Neuropathy grading

- Peripheral sensory neuropathy grading by CTCAE
- QLQ-CIPN20 grading

APPENDIX E: Ideal Body weight (IBW)

• Color-coded Ideal Body Weight (IBW) tables for male and female subjects
